## Synopsis

Title	Procalcitonin-guided treatment regarding antibiotic use for acute COPD exacerbations: a prospective randomized controlled trial
Short title	PRECISION study
Clinical study phase	IV

## Summary

Study objectives
	
The primary objective of this study is to show that at hospitalization for a severe exacerbation of COPD, PCT-guided treatment regarding antibiotic use is non-inferior to usual care consisting of prednisolone and or antibiotics, in terms of treatment failure at day 30 for patients hospitalized because of an acute exacerbation of COPD (AECOPD). Treatment failure is defined as disease-related mortality, endotracheal intubation, vasopressors, renal failure, lung abscess/empyema, pneumonia development or hospital readmission within 30 days after inclusion of the study.
 
The secondary objectives of this study are to assess the following secondary endpoints:
 
 
• Treatment failure defined as an incomplete resolution of the clinical signs and symptoms associated with the AECOPD at day 30 after inclusion of the study (i.e not reaching the baseline condition prior to the AECOPD) scored using the modified Anthonisen criteria.
 
• Change in Quality of Life on day 1, 10, and after 30 days using the COPD Assessment Test (CAT)
 
• Start of antibiotic therapy after an initial opposite decision (after 48 hours)
 
• Side effects (gastro-intestinal complaints, allergic reactions)
 
• Cumulative antibiotic consumption
 
• Cumulative prednisolone consumption
 
• Length of hospitalization
 
• Time to complete resolution of symptoms according to daily symptom diaries evaluating the modified Anthonisen criteria
 
• Re-exacerbation within 30 days
 
• PROM symptom score: EXACT – Respiratory symptoms scale (at admission, at day 10 and at day 30 after admission)
 
• Non-Invasive ventilation after 72 hours of admission
 

Test drug Name of active ingredient
 
Dose
 
Route of administration
 
Duration of treatment
	
Amoxicillin-clavulanic acid or doxycycline (in case of a bêtalactam or penicillin allergy) 875/125mg three times a day and 100mg once daily (200 mg on the first day), respectively
 
Oral
 
5 days

Indication
	
Severe acute exacerbation of COPD (i.e. with hospitalization)


Diagnosis and main criteria for inclusion
	
Inclusion criteria
 
 
- COPD, according to GOLD 2018 definition
 
- Hospitalization because of severe acute exacerbation of COPD
 
- Post-bronchodilator FEV1/FVC < 0,70 and FEV1% < 80%pred. within last 5 years
 
- At least 40 years of age
 
- Smokers or ex-smokers with <math>\geq 10</math> packyears
 

	
 
- Written informed consent
 
- Start of symptoms within 7 days before admission
 
- Presence of at least 2 major symptoms of the modified Anthonisen criteria (acute deterioration in sputum volume, sputum purulence and dyspnea) or the presence of 1 major symptom and 1 minor symptom (coughing, wheeze, nasal discharge, sore throat, fever)
 
 
Exclusion criteria
 
 
- Indication for ICU and or non-invasive ventilation < 72h of admission
 
- Pneumonia, radiologically confirmed
 
- Infection at another site and/or sepsis according to the SIRS criteria (with tachycardia and tachypnea not being caused by the exacerbation).
 
- COPD before age 40.
 
- Asthma, without presence of COPD. 
 
o Patients with COPD , with or without a history of asthma (in childhood or as an adolescent) will NOT be excluded/are allowed to participate.
 
o Patients with Asthma/COPD overlap syndrome (with current asthma AND COPD) will NOT be excluded/are allowed to participate.
 
 
 
- Clinically relevant heart failure or myocardial ischemia
 
- Chronic use of immunosuppressants, including prednisolone (prednisone equivalent of 10mg or less is NOT an exclusion criterion).
 
- Known bronchiectasis as a primary diagnosis
 
- Colonisation with Pseudomonas spp. or other micro-organisms in recent cultures (last 60 days) not susceptible to amoxicillin-clavulanic acid
 
- Pregnancy
 
- Recent exacerbation (last 28 days)
 

Study design	Prospective randomized controlled trial
Methodology	Hospital based clinical trial
Type of control	Usual care, in which the physician decides on clinical reasons to prescribe prednisolone and or antibiotics
Number of subjects	678
Primary variabel	Treatment failure at day 30
Plan for statistical analysis	
Primary analysis The primary endpoint is defined as 30-day treatment failure. The per protocol (PP) population is the main analysis population. The difference and corresponding 95% confidence interval (two-sided) in the incidence of the primary endpoint between the randomly allocated strategies (biomarker-guided antibiotic use minus usual care) will be determined. Non-inferiority will be concluded if the upper limit of this confidence interval does not exceed the prespecified non-inferiority margin of 5%.
 
Secondary analyses Differences in the incidence of these secondary endpoints between randomly allocated strategies will be analyzed by chi-square tests and logistic regression.

---

## 1. INTRODUCTION AND RATIONALE

Chronic obstructive pulmonary disease (COPD) is a prevalent disease, worldwide, and in the Netherlands with approximately 600.000 patients. COPD is currently the 4th leading cause of death worldwide and it is estimated to be the 3rd leading cause in 2020 (1-3). It is also a leading cause of disability-adjusted life years and with increasing prevalence the loss will also increase. The burden on health-care system is therefore impressing: COPD accounts for just over 3% of the total health care budget in the European Union. The majority of these costs are attributed to acute exacerbations of COPD (AECOPD) (4).

Reducing the burden of disease for patients (mortality and disability adjusted life years) and for society (costs) of this leading chronic disease is therefore of paramount importance. Given the contribution of exacerbations both to loss in quality of life and to costs, it is of major importance to improve the current treatment of exacerbations. Treatment of AECOPD generally consists of corticosteroids to reduce airway inflammation and antibiotics to treat bacterial infections, mostly in one-size fits all fashion.

Pulmonary physicians are well aware of overuse of both antibiotics and of prednisolone, but lack the tools to decide which medication to give on in the clinical setting. As a consequence, in the Netherlands 65% of patients hospitalized for COPD receive antibiotics (Landelijk Zorgpad COPD 2018). This overuse is important not only for the costs incurred for giving useless therapy, but there are also major side effects, the more frequent ones being gastrointestinal complaints. Finally, the overuse of antibiotics results in induction of antibiotic resistance, a worldwide grave concern.

Biomarkers may aid towards a more personalized treatment of AECOPD by identifying which patient would benefit from antibiotics. Procalcitonin (PCT) is the precursor of calcitonin and is released in response to a bacterial infection within 6-12 hours by many tissues under stimulation of several cytokines. Procalcitonin levels are minimally raised in viral infections (5), making it a relative specific diagnostic tool for bacterial infections. Several trials have shown a reduction in antibiotic consumption in AECOPD when using a PCT-guided treatment algorithm (6-9). One meta-analysis about the use of PCT to guide antibiotic administration in AECOPD suggested that PCT-based protocols may be superior to standard care in a mixed group of patients and indications (10). In this meta-analysis 7 of the 8 included trials, including trials performed by Stolz et al. (Chest 2007), Verduri et al. (PLoS ONE 2015) and Corti et al. (Int J of COPD 2016) recommended starting antibiotic therapy for procalcitonin levels  $> 0.25\mu\text{g/L}$  (or  $0.25\text{ng/mL}$ ), (6a,b,c) This meta-analysis included the before mentioned study by Schuetz et al. (6). To be able to compare our results to these important international studies we decided to use the same cut-off value. The quality of the data of the meta-analysis was judged low to moderate, necessitating appropriately powered confirmatory trials before recommending introducing such strategies in daily clinical practice (10).

In summary, PCT has not been tested in a clinical setting in a treatment algorithm specifically in COPD with the primary outcome measure being treatment failure.

## 2. OBJECTIVES

We hypothesize that at hospitalization for a severe acute exacerbation for COPD, biomarker-guided treatment based on procalcitonin level to guide antibiotic administration is non-

---

inferior to usual care consisting of prednisolone and or antibiotics, which is based on a clinical decision, in terms of treatment failure at day 30.

The secondary objectives are to establish that a biomarker-guided decision algorithm results in an improvement in quality of life, a decrease in consumption of antibiotics, and a reduction of important side effects.

### 3. STUDY DESIGN

Study design: prospective randomized controlled trial.

Patients will be randomized to biomarker-guided treatment (based on blood procalcitonin level) or to usual care. In the usual care arm, and in the biomarker guided-arm in case of high procalcitonin, patients will receive amoxicillin-clavulanic acid.

Prednisolone will be given during 5 days and with a dose of 40mg/day in a single dose as recommended by the Dutch National Guideline (16).

Usual care	Physician's choice	Prednisolone ± antibiotics
PCT level guided care	PCT ≤ 0.25ug/L	Prednisolone
	PCT > 0.25ug/L	Prednisolone + amoxicillin-clavulanic acid

The procalcitonin will be measured in both groups but will only be reported for the patients randomised to the PCT group and not for patients in the usual care group during the study period. The measurement will be performed in the usual care group but this will be blinded until the study is completed.

### 4. STUDY POPULATION

#### 4.1 Population (base)

Patients with a severe exacerbation of COPD, defined according to the GOLD criteria (3) and modified Anthonisen criteria (13,14), for which they need to be hospitalized.

#### 4.2 Inclusion criteria

- COPD, according to GOLD 2018 definition
- Indication for hospitalization because of acute severe exacerbation of COPD, as defined by GOLD 2018 and modified Anthonisen criteria (13,14)
- Presence of at least 2 major symptoms of the modified Anthonisen criteria (acute deterioration in sputum volume, sputum purulence and dyspnea) or the presence of 1 major symptom and 1 minor symptom (coughing, wheeze, nasal discharge, sore throat, fever)
- Post-bronchodilator FEV1/FVC < 0,70 and FEV1% < 80%pred. within last 5 years
- At least 40 years
- Smokers or ex-smokers with ≥ 10 packyears
- Written informed consent
- Start of symptoms no more than 7 days before admission

---

### 4.3 Exclusion criteria

- Indication for ICU and or non-invasive ventilation < 72h of admission
- Pneumonia, radiologically confirmed
- Infection at another site and/or sepsis according to the SIRS criteria (with tachycardia and tachypnea not being caused by the exacerbation).
- COPD before age 40.
- Asthma, without presence of COPD.
  - Patients with COPD , with or without a history of asthma (in childhood or as an adolescent) will NOT be excluded/are allowed to participate.
  - Patients with Asthma/COPD overlap syndrome (with current asthma AND COPD) will NOT be excluded/are allowed to participate.
- Clinically relevant heart failure or myocardial ischemia
- Chronic use of immunosuppressants, including prednisolone (a prednisone equivalent of 10mg or less is allowed/is NOT an exclusion criterion)
- Known bronchiectasis as a primary diagnosis
- Colonisation with *Pseudomonas* spp. or other micro-organisms in recent cultures (last 60 days) not susceptible to amoxicillin-clavulanic acid
- Pregnancy
- Recent exacerbation (last 28 days)

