#### 8.1.2 Secondary study parameters/endpoints

The secondary objectives of this study are to assess the following secondary endpoints:-

The key secondary objective is:

- Treatment failure defined as an incomplete resolution of the clinical signs and symptoms associated with the AECOPD at day 30 after inclusion of the study (i.e not reaching the baseline condition prior to the AECOPD) scored using the modified Anthonisen criteria.

The other secondary objectives are:

- Change in Quality of Life on day 1, 10, and after 30 days using the COPD Assessment Test (CAT)
- Decision to start antibiotic therapy after an initial opposite decision (after 48 hours)
- Side effects (gastro-intestinal complaints, allergic reactions)
- Cumulative antibiotic consumption
- Cumulative prednisolone consumption
- Length of hospitalization
- Time to complete resolution of symptoms according to daily symptom diaries evaluating the modified Anthonisen criteria
- Re-exacerbation within 30 days
- PROM symptom score: EXACT – Respiratory symptoms scale (at admission, at day 10 and at day 30 after admission)
- Non-Invasive ventilation after 72 hours of admission

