**8.2 Randomisation, blinding and treatment allocation**

Upon presentation at the emergency department, patients will be clinically judged for in- and exclusion criteria, among which indication for hospitalization. When eligible the patient will be notified about the study. When the patient is interested in participating, the patient information form will be discussed by the treating physician. The participation being voluntarily and the opportunity to discontinue participation will be made clear by the treating physician. Informed consent will be requested with at least two hours of time to decide. Randomisation will occur by a computer-based program. We will use a block-randomisation with randomly alternating blocks of 4 or 6 patients (random permuted block randomisation) and with stratification by center and with stratification by pre-treatment with antibiotics. The patient will not be blinded for the treatment received (prednisolone with or without antibiotic therapy) but the patient will be blinded for the treatment strategy (usual care or PCT-guided treatment). The participating centers will appoint two physicians that will be outcome assessors. The outcome assessors will be blinded for the treatment strategy.

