### **Statistical and analytical plans**

#### **Primary analysis**

The primary endpoint is defined as 30-day treatment failure. The per protocol (PP) population is the main analysis population. An analysis will be performed for the randomly

---

allocated antibiotic strategy (i.e. usual care versus antibiotics in patients with PCT >0.25 µg/L). The difference and corresponding 95% confidence interval (two-sided) in the incidence of the primary endpoint between the randomly allocated strategies (biomarker-guided drug use minus drug-in-all) will be determined. Non-inferiority will be concluded if the upper limit of the 95% confidence interval does not exceed the prespecified non-inferiority margin of 5%.

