6.1 General Study Design and Plan

- Study design: prospective, randomized-controlled trial. Patients will be randomized to biomarker-guided treatment (based on blood procalcitonin level) or to usual care. In the usual care arm, and in the biomarker guided-arm in case of high ($> 0.25\mu\text{g/L}$) procalcitonin, patients will receive amoxicillin-clavulanic acid.
- Type of Comparison: non-inferiority.
- Type of control(s): usual care
- Level and method of blinding (e.g. double-blind): The patient and the outcome assessor will be blinded for the allocated treatment strategy. Two independent physicians will be selected per center to be the outcome assessors. The patient will not be blinded for the treatment itself (prednisolone with or without antibiotic therapy).
- Method of treatment assignment: We will use a block-randomisation with randomly alternating blocks of 4 and 6 patients (random permuted block randomisation). The randomisation will be stratified per center.
- At what point in time subjects are randomized relative to treatments, events and study periods: Upon presentation at the emergency department, patients will be clinically

judged for in- and exclusion criteria, among which indication for hospitalization. When eligible the patient will be notified about the study. When the patient is interested in participating, the patient information form will be discussed by the treating physician. The participation being voluntarily and the opportunity to discontinue participation will be made clear by the treating physician. Informed consent will be requested with at least two hours of time to decide

- Sequence and duration of all study periods: screening will occur on the first day of admission as described above, baseline characteristics will be collected within 24 hours of admission, active treatment will be 5 days, follow-up will be 30 days.

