8.2.2 Per Protocol Population

- All subjects who:
 - met all inclusion/exclusion criteria,
 - attained a sufficient compliance to the treatment received, treatment with prednisolone and/or antibiotics, when prescribed on admission for at least 5 days,
 - did not present serious deviations from the protocol.

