10.2 Secondary Efficacy Analyses

10.2.1 Secondary Analyses of Primary Efficacy Endpoint

Our primary analysis population will be the per-protocol population because of the non-inferiority design. The secondary analysis population will be the intention-to-treat analysis.

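### The ICU/NIV exclusion runs to hour 72, past day-1 randomisation, and nothing stops it from removing early treatment failures from the primary per-protocol analysis

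*Protocol*

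**What the plan says.** **The criterion.** Protocol 4.3 excludes patients with "Indication for ICU and or non-invasive ventilation < 72h of admission". SAP 6.2 lists the same item.

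**When eligibility is judged.** Protocol 8.2 states: "Upon presentation at the emergency department, patients will be clinically judged for in- and exclusion criteria". SAP 6.1 adds: "screening will occur on the first day of admission as described above, baseline characteristics will be collected within 24 hours of admission". The schedule in Protocol 8.3 places randomisation in the Day 1 column only.

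**Who is in the primary analysis.** Protocol section 10 and SAP 8.2.2 both require PP patients to have "met all inclusion/exclusion criteria". Under the primary analysis the protocol says: "The per protocol (PP) population is the main analysis population". SAP 10.2.1 says: "The secondary analysis population will be the intention-to-treat analysis".

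**What counts as an outcome.** Protocol 8.1.1 counts intubation and vasopressor use as treatment failure over 30 days from inclusion, with no lower time limit. A secondary endpoint is "Non-Invasive ventilation after 72 hours of admission", and Protocol 10.2 adds ICU admission with the same 72-hour start.

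**The concern.** A criterion that can be met or breached by something that happens after allocation is not a baseline criterion. If it also decides membership of the primary analysis set, patients can leave that set because of an outcome the strategy may have caused.

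Here the overlap is direct. An ICU course within 72 hours can include intubation or vasopressors, both of which are components of the primary endpoint. SAP 8.5.1 describes the harm the trial must rule out: a patient whose PCT is falsely low goes without antibiotics and deteriorates, possibly to ICU admission or death. If that happens in the first three days, the plan allows the patient to be classed as ineligible instead of as a failure. SAP 8.5.4 names PP as the main population within the interim-analysis section, so the interim look may be affected in the same way.

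Because the text permits two readings, whoever builds the PP set would have to choose between them, possibly with outcomes known.

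**Working it through.** **1. The passages side by side.** Take a patient randomised on day 1 and intubated at hour 48.

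- Protocol 8.1.1: treatment failure, since the event falls within 30 days of inclusion.
- Protocol 4.3 / SAP 6.2: had an ICU indication before hour 72, so meets an exclusion criterion.
- Protocol 10 / SAP 8.2.2: did not satisfy all eligibility criteria, so not in PP.
- SAP 9.3 (deviations): silent. The PP removal it spells out is for antibiotics given despite a low PCT.
- Protocol 8.4.1 (withdrawal criteria): not applicable.

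The endpoints that start at 72 hours fit a reading in which hours 0 to 72 belong to eligibility and later hours to outcome.

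**2. The plan's own figure.** Inputs from Protocol 4.4: 20.4% failure in usual care, 16.7% in the PCT arm, 5-point margin, one-sided alpha 0.025, power 80%.

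n per arm = [0.204×0.796 + 0.167×0.833] × (1.960 + 0.842)² / (0.05 + 0.037)² = 312.6, so 313 per arm and 626 in total, as stated. At the final two-sided level of 0.0492 (Protocol 10.4) the same formula gives 314.2, so 315 per arm, also as stated.

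**3. Effect of removal on the error rate.** True rates are set exactly at the margin: 25.4% (PCT) versus 20.4% (usual care), 315 per arm. Assumptions, not in the documents:

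- e = share of randomised patients with an ICU/NIV indication after randomisation and before hour 72;
- s = share of those patients who are also primary failures.

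The share s matters because NIV or ICU admission alone is not a component of the primary endpoint.

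- PP failure rate in an arm = (p − s·e)/(1 − e), with 315(1 − e) patients left.
- P(non-inferiority) = Φ[(0.05 − d)/SE − 1.960], where d is the PP difference and SE its unpooled standard error. This follows the protocol's risk-difference criterion.

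Worked case, e = 2% (usual care) and 4% (PCT), s = 100%:

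- usual care (0.204 − 0.02)/0.98 = 18.8%, n = 308.7;
- PCT (0.254 − 0.04)/0.96 = 22.3%, n = 302.4;
- d = 3.5 points, SE = 3.27 points;
- Φ[(5.0 − 3.52)/3.27 − 1.960] = 6.6%.

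| e, usual care / PCT | s | PP difference (points) | False non-inferiority |
|---|---|---|---|
| nothing removed | – | 5.0 | 2.5% |
| 2% / 4% | 100% | 3.5 | 6.6% |
| 2% / 4% | 50% | 4.6 | 3.3% |
| 2% / 4% | 25% | 5.1 | 2.3% |
| 2% / 2% | 100% | 5.1 | 2.3% |

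In the 2% / 4% case the inflation disappears at about s = 30%. Below that, removal is slightly conservative.

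**The case against.** **Eligibility is judged at entry.** Protocol 8.2 has patients assessed in the emergency department, before consent and randomisation, and the criterion speaks of an indication, not of receiving ICU care or NIV. No passage says eligibility is re-judged at 72 hours. Protocol 8.4 expects investigator withdrawals for safety mostly to be treatment failures, which points towards counting such patients. This stands as a possible reading, so one cannot say that the plan definitely deletes early deteriorations. But it leaves the 72-hour limit with little to do, the endpoints that start at 72 hours point the other way, and nothing rules out the other reading.

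**ITT keeps these patients.** Dosed patients stay in ITT, and a gap between PP and ITT would show. This stands, but ITT is secondary and the non-inferiority conclusion is drawn from PP.

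**Three stronger readings that the documents do not support:**

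- *That ICU care or NIV in the first three days is recorded nowhere.* SAP section 11 collects adverse events from consent to day 30. Its tables list ICU admission and respiratory failure with need for NIV, and SAP 11.2 names both among the events of interest. The early hours are missing only from the NIV and ICU efficacy endpoints.
- *That removal always favours non-inferiority.* It does so only if early failures are more frequent in the PCT arm and enough of the removed patients are primary failures.
- *That the bias is known to be large.* With 2% / 7% early patients, all of them primary failures, false non-inferiority would be 24%. That case places the whole 5-point excess in the first 72 hours. With the same rates it is 5.6% if half are failures and 2.3% if a quarter are.

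**Conclusion.** The concern holds as an unresolved conflict in the text that bears on the primary analysis set. As written, an early intubation or vasopressor event can be both a primary failure and a ground for removal from PP.

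The direction of bias is conditional: towards non-inferiority if early failures are more frequent under PCT guidance, and none with equal removal. The size cannot be derived from the documents. Under the assumed 2% versus 4% early ICU/NIV rates, the one-sided error ranges from about 2.3% to 6.6% against a nominal 2.5%, depending on how many of those patients are primary failures. It rests on true rates exactly at the margin, 315 per arm and a risk-difference analysis.

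The case for action does not depend on that figure. Membership of a confirmatory analysis set should not turn on an event after randomisation that overlaps the primary endpoint.

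**What to change.** Reconcile Protocol 4.3 and SAP 6.2 with Protocol 8.1.1, 8.2 and 10 and with SAP 8.2.2. Two statements are enough:

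1. In Protocol 10 and SAP 8.2.2: eligibility for the PP population is judged only on information available before randomisation.
2. In the same places: a need for ICU care or NIV that first arises after randomisation is not an eligibility violation. The patient stays in PP, and any primary component event counts.

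Make this change before anyone builds the PP set with outcomes in view, which includes the interim analysis.

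The clinical threshold for the exclusion is the sponsor's decision. Moving the 72-hour start of the NIV and ICU secondary endpoints would be a separate redefinition and is not needed here.

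Cost: one or two sentences of wording. No extra patients or data are needed, because the events concerned are already collected.
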